7.3.3 Safety analyses

All subjects who received one dose of study drug will be included in the safety evaluation.

Safety analyses will focus on adverse events related to early discontinuation, immune suppression and injection site effects. AEs will be coded using the Medical Dictionary for Drug Regulatory Affairs (MedDRA). All AEs occurring up to 12 weeks after the last trial medication administration will be assigned to the treatment period for evaluation. The evaluation of adverse events will comprise various frequency tabulations. The additional analyses of pre-defined AESI will consider the frequency, intensity, time to first onset of the AE, duration of the AE and clinical consequences (e.g. study discontinuation).

Analysis of laboratory measures will similarly focus on hematologic measures of immune suppression. Descriptive statistics of laboratory values over time and for the difference from baseline will be provided. Frequency tables of changes with respect to the reference range between baseline and last/worst value on treatment and patients with possible clinically significant abnormalities will also be presented.

Immunogenicity will be evaluated in terms of time to antibody emergence starting from the time of first exposure to BI 655066 in either 1311.2 or 1311.13. This will be analysed using a Kaplan-Meier estimate.

Safety will also be assessed by evaluation of vital signs (BP, PR, RR, oral or tympanic body temperature) and local tolerability.

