7. "xT" is a targeted physical examination including assessment of vital sign measurements, and evaluation of organ systems associated with AE(s) symptoms or laboratory abnormalities.
8. Measured after 5 minutes of rest in the supine position. Measurements of vital signs should, if possible, always precede blood sampling.
 - a. Extended visit 1: Vital signs will be taken ~ 30 min pre-dose, 5 minutes, and 1 hour after the dose is administered
 - b. Following dosing visits: Vital signs will be taken ~ 30 min pre-dose, 5 minutes, and 1 hour after the dose is administered
 - c. Non-dosing visit (Extended EOS): Vital signs will be measured once per visit
9. ECG to be performed after 5 minutes of rest in the supine position, at every 24 weeks, starting from EV1 (EV1, EV3, EV5...). Should, if possible, be performed prior to blood sampling.
10. Not to be performed for patients who prematurely discontinue the treatment period.
11. All new AEs as well as unresolved AE from the preceding trial 1311.2 should be followed up within this study.
12. Only for patients with psoriatic arthritis.
13. For details of laboratory tests cf. [Section 5.2.3](#), [Table 5.2.3:1](#) and [5.2.3.2](#)
14. Patients must be fasting for at least 8 hours prior to collection of the safety laboratory samples.
15. Only applicable for women of childbearing potential.
16. In women of childbearing potential urine pregnancy test has to be performed before each administration of study drug.
17. Blood samples for protein biomarker, PK and ADA will be drawn ~ 30 min before the subcutaneous injection (PreD) at every 24 weeks, starting from EV1 (EV1, EV3, EV5...).
18. For patients who prematurely discontinue the follow up period before study end (for any reason), an early Extended EOS visit is required. This early Extended EOS visit will include the same procedures as the normal Extended EOS visit.
19. Patients will be asked to give consent to be contacted (or for their primary care physician to be contacted) by the study team to obtain vital status information preferably at the time of study entry
20. Only required at EV1 for patients who are having EV1 as their first 1311.13 visit
21. All efficacy assessments should be performed pre-dose (PreD)
22. To be repeated once per year until study end (EV1, EV5, EV10...)

Proprietary confidential information.

© 2018 Boehringer Ingelheim International GmbH or one or more of its affiliated companies. All rights reserved.

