3.3 SELECTION OF TRIAL POPULATION

Eligible patients from trial 1311.2 will be offered participation in this OLE trial. The check for patient eligibility will be based upon a successful completion (cf. [Section 3.3.2](#)) of the previous trial and on signing the Informed Consent for the OLE.

A 40 % dropout rate from preceding trial is expected, leaving approximately 100 patients to be entered in this trial.

A log of all patients included into the study (i.e. having given informed consent) will be maintained in the ISF at the investigational site.

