## **5.0 Analysis Populations**

### **5.1 Definition for Analysis Populations**

#### **Intent to Treat (ITT) Populations:**

The ITT Population is defined as all subjects who receive at least one dose of study drug in the study.

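### Time to antibody emergence: plain Kaplan-Meier from first exposure in either trial places onset late, and its pre-entry part is conditional on roll-over

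*Protocol*

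**What the plan says.** Protocol 7.3.3 (and 5.2.1.3, with the same content) sets the clock for antibody emergence: "Immunogenicity will be evaluated in terms of time to antibody emergence starting from the time of first exposure to BI 655066 in either 1311.2", and the sentence goes on to name 1311.13 as the alternative. The estimator follows: "This will be analysed using a Kaplan-Meier estimate". Neither section mentions delayed entry, interval censoring or how a patient already positive on entry is dated.

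The analysis set is limited to patients treated here. Protocol 7.3.3 says "All subjects who received one dose of study drug will be included in the safety evaluation". SAP 5.1 makes this specific, "The ITT Population is defined as all subjects who receive at least one dose of study drug in the study", and uses the same set for safety.

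On sampling, Flow Chart footnote 17 says "Blood samples for protein biomarker, PK and ADA will be drawn ~ 30 min before the subcutaneous injection (PreD) at every 24 weeks", counted from EV1. The chart also marks ADA at the Extended end-of-treatment and end-of-study visits.

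On who enters, Protocol 3.3 says "A 40 % dropout rate from preceding trial is expected". Exclusion criterion 1 removes patients with a drug-related serious adverse event in 1311.2. Inclusion criterion 1 admits both those who completed follow-up and those who lost response (below PASI50) from week 24.

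The SAP contains no immunogenicity analysis: Section 11.1 does not list it, Table 1 has no ADA window, and Sections 12 and 13 leave out pharmacokinetics and biomarkers. That omission is a separate matter; the point here is the method the protocol prescribes.

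**The concern.** The time origin, the analysis set and the sampling schedule do not fit a plain Kaplan-Meier estimate.

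- **Dating.** Nobody observes the day an antibody appears. The data give an interval from the last negative to the first positive sample. A patient positive at EV1 with no earlier sample is left-censored. Kaplan-Meier needs an exact date and in practice takes the date of the positive sample, which is always at or after the true onset.
- **Selection.** For a patient first exposed in 1311.2, the time between that exposure and entry is seen only because the patient later rolled over. The early part of the curve describes all exposed patients only if roll-over is unrelated to ADA status. The entry rules depend on drug-related serious events and on loss of response, and either could be related to antibodies.

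Immunogenicity is among the additional objectives in Protocol 2.2. A curve labelled as time from first exposure would be read as incidence and onset in treated patients generally, and it may be neither.

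**Working it through.** Neither document gives an ADA rate, a precision target or a worked figure, so there is nothing to reproduce. All ADA rates below are assumptions.

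**1. Share of entrants whose clock starts before entry.** Protocol 2.3 says 75% of 1311.2 patients receive BI 655066 there. If all arms roll over at the same rate, the share among entrants is 75%. If those patients roll over at *a* times the rate of the rest, the share is 0.75a / (0.75a + 0.25). For a = 0.8 this is 0.60/0.85 = 71%; for a = 1.25 it is 0.9375/1.1875 = 79%. The remaining quarter or so are first exposed here and have no pre-entry period on drug.

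**2. Time from 1311.2 start to entry.** Protocol 6.2.1 gives roll-over at weeks 24 to 44 (loss of response) or week 48 (completion). Protocol 3.1 allows up to 6 weeks between the trials. The range is 24 to 48 + 6 = 54 weeks. For patients already in this study when the extended schedule was introduced, EV1 falls later than entry. The documents show no ADA sampling schedule for that earlier period.

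**3. Dating error, closed form.** If onset is uniform over an interval of width *w*, dating at the positive sample is late by w/2 on average and at most w.
- Between extended-period samples, w = 24: mean 12 weeks, maximum 24.
- Positive at EV1, no 1311.2 sample used, EV1 at entry, w = 24 to 54: mean 12 to 27 weeks, maximum 54.

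**4. Dating error, simulation.** Assumptions: constant hazard with 10% ADA by week 48, ADA persistent, 75% first exposed in 1311.2, 30% of those entering at weeks 24 to 44 and the rest at week 48, 24-weekly samples from EV1, and roll-over unrelated to ADA.
- Mean delay is 14.3 weeks with 1311.13 samples only.
- It is 10.9 weeks if 12-weekly samples from 1311.2 are added (that schedule is assumed).

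Cumulative incidence, 1311.13 samples only:

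| Week from first exposure | Kaplan-Meier | True |
|---|---|---|
| 47 | 2.9% | 9.8% |
| 48 | 9.6% | 10.0% |
| 144 | 26.7% | 27.1% |
| 192 | 34.1% | 34.4% |

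The curve is too low between sampling times and nearly right at them.

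**5. Selection.** Let p be the true ADA proportion by roll-over among patients first exposed in 1311.2, and k the roll-over rate of ADA-positive relative to ADA-negative patients. The proportion among those who roll over is pk / (pk + 1 − p); the overall roll-over rate cancels.

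| p | k = 0.5 | k = 1 | k = 1.5 |
|---|---|---|---|
| 5% | 2.6% | 5.0% | 7.3% |
| 10% | 5.3% | 10.0% | 14.3% |
| 20% | 11.1% | 20.0% | 27.3% |

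For example, p = 10% and k = 1.5 gives 0.15/1.05 = 14.3%. In the simulation, which includes the quarter first exposed here, the week-48 estimate is 6.3% for k = 0.5 and 12.6% for k = 1.5, against a true 10.0%. At week 144 it is 24.2% and 29.2%, against 27.1%. The documents give no value for k.

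**The case against.** A reader might infer that cumulative ADA incidence is biased low, because 40% of 1311.2 patients are expected not to enter and drug-related serious events exclude. The documents do not support a direction. Loss of response is itself an entry route and could bring in more antibody-positive patients. No criterion bars an ADA-positive patient from entry, so events before entry are not lost by design; they count if ADA persists to EV1 or if 1311.2 samples are used. For the same reason this is not strict left truncation, in which patients with an earlier event could not be observed at all. The 40% figure also covers all 1311.2 arms together.

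A reader might also infer that 24-weekly sampling lowers incidence. With persistent ADA and no selection it mainly shifts onset. A large loss needs a further assumption. If ADA lasts only 12 weeks and only 1311.13 samples are used, ever-positive incidence at week 144 reads 11.7% against 27.1%. If EV1-positive patients are dropped without adjustment, it reads 21.4% against 27.1%. The documents state neither condition.

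Finally, ADA is a further endpoint, assessed descriptively and without testing, and the SAP has yet to include it. That is fair and limits the weight of the point. It does not remove the late dating, which needs no assumption about selection.

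**Conclusion.** The point holds for dating and, as an unquantified risk, for selection. Late onset follows directly from the prescribed method: about 12 weeks on average within a 24-week interval if onset is uniform, and possibly more for patients already positive at EV1 if 1311.2 samples are not used. The documents do not say whether those samples enter the analysis or what their schedule was, so no single figure can be given for the pre-entry period.

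For patients first exposed in 1311.2, the curve before entry is conditional on roll-over. The resulting bias in incidence is zero if roll-over is unrelated to ADA and can otherwise go either way. This is a minor point for a descriptive analysis, but it should be settled before the analysis is written.

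**What to change.** When the ADA analysis is added to the SAP:

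1. Replace plain Kaplan-Meier with an interval-censored (Turnbull) estimate, each event lying between the last negative and the first positive sample. Treat EV1-positive patients without earlier samples as left-censored.
2. State whether 1311.2 ADA samples are used.
3. Report ADA prevalence at EV1, and a curve from first dose in this study among patients ADA-negative at EV1. For patients dosed here before their EV1, define the origin so that the clock and the negative sample coincide.
4. Label any curve from first exposure in 1311.2 as conditional on roll-over.

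Adding all risankizumab-treated 1311.2 patients would remove the conditioning. It would also rest on ADA data that these documents do not describe, and would change the question from an extension-study analysis to a cross-trial one, so it is not needed here.

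The cost is a little more analysis work and wider, more honest uncertainty about onset. No change to visits or sampling is required.

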7.3.4 Interim analyses

Results will be analysed periodically by the sponsor and DMC in order to review the accumulating safety data of BI 655066 in psoriasis.

7.3.5 Pharmacokinetic analyses

Individual concentration-time data with descriptive statistics for trough concentrations will be presented in the clinical trial report.

Population pharmacokinetic/pharmacodynamic analysis, if performed, will be reported separately.

7.3.6 Pharmacodynamic analyses

Serum/plasma biomarkers will be summarized over time and correlated with clinical endpoints (i.e. PASI, PGA).

7.3.7 Pharmacogenomic analyses

Not applicable.

7.4 HANDLING OF MISSING DATA

Use of inappropriate concomitant medication to treat psoriasis will be considered as failure when deriving response variables, e.g. PASI₉₀.

Further details on the handling of missing data will be provided in the Trial Statistical Analysis Plan.

7.5 RANDOMISATION

There is no randomisation for this study. All patients will be assigned to the same regimen and dose of BI 655066, regardless of the treatment and dose received in the 1311.2 study.

7.6 DETERMINATION OF SAMPLE SIZE

The sample size is determined by the completion of previous trial and the consenting for the extension.

Proprietary confidential information.

© 2018 Boehringer Ingelheim International GmbH or one or more of its affiliated companies. All rights reserved.

This document may not - in full or in part - be passed on, reproduced, published or otherwise used without prior written permission.

8. INFORMED CONSENT, DATA PROTECTION, TRIAL RECORDS

The trial will be carried out in compliance with the protocol, the principles laid down in the Declaration of Helsinki, in accordance with the International conference on harmonisation (ICH) Harmonised Tripartite Guideline for Good Clinical Practice (GCP) and relevant BI Standard Operating Procedures (SOPs). Standard medical care (prophylactic, diagnostic and therapeutic procedures) remains in the responsibility of the treating physician of the patient.

The investigator should inform the sponsor immediately of any urgent safety measures taken to protect the study subjects against any immediate hazard, and also of any serious breaches of the protocol/ICH GCP.

The rights of the investigator and of the sponsor with regard to publication of the results of this trial are described in the investigator contract. As a general rule, no trial results should be published prior to finalisation of the Clinical Trial Report.

Insurance Cover: The terms and conditions of the insurance cover are made available to the investigator and the patients via documentation in the ISF (Investigator Site File).

8.1 STUDY APPROVAL, PATIENT INFORMATION, AND INFORMED CONSENT

This trial will be initiated only after all required legal documentation has been reviewed and approved by the respective Institutional Review Board (IRB) / Independent Ethics Committee (IEC) and competent authority (CA) according to national and international regulations. The same applies for the implementation of changes introduced by amendments.

Prior to patient participation in the trial, written informed consent must be obtained from each patient (or the patient's legally accepted representative) according to ICH GCP and to the regulatory and legal requirements of the participating country. Each signature must be personally dated by each signatory and the informed consent and any additional patient-information form retained by the investigator as part of the trial records. A signed copy of the informed consent and any additional patient information must be given to each patient or the patient's legally accepted representative.

The patient must be informed that his/her personal trial-related data will be used by Boehringer Ingelheim in accordance with the local data protection law. The level of disclosure must also be explained to the patient.

The patient must be informed that his / her medical records may be examined by authorised monitors (CML/CRA) or Clinical Quality Assurance auditors appointed by Boehringer Ingelheim, by appropriate IRB / IEC members, and by inspectors from regulatory authorities.

8.2 DATA QUALITY ASSURANCE

A quality assurance audit/inspection of this trial may be conducted by the sponsor or sponsor's designees or by IRBs/IECs or by regulatory authorities. The quality assurance

Proprietary confidential information.

© 2018 Boehringer Ingelheim International GmbH or one or more of its affiliated companies. All rights reserved.

This document may not - in full or in part - be passed on, reproduced, published or otherwise used without prior written permission.

auditor will have access to all medical records, the investigator's trial-related files and correspondence, and the informed consent documentation of this clinical trial.

8.3 RECORDS

Case Report Forms (CRFs) for individual patients will be provided by the sponsor, either on paper or via remote data capture. For drug accountability, refer to [Section 4.1.8](#).

8.3.1 Source documents

Source documents provide evidence for the existence of the patient and substantiate the integrity of the data collected. Source documents are filed at the investigator's site.

Data entered in the eCRFs that are transcribed from source documents must be consistent with the source documents or the discrepancies must be explained. The investigator may need to request previous medical records or transfer records, depending on the trial; also current medical records must be available.

For eCRFs all data must be derived from source documents.

8.3.2 Direct access to source data and documents

The investigator / institution will permit trial-related monitoring, audits, IRB / IEC review and regulatory inspection, providing direct access to all related source data / documents. CRFs/eCRFs and all source documents, including progress notes and copies of laboratory and medical test results must be available at all times for review by the sponsor's clinical trial monitor, auditor and inspection by health authorities (e.g. Food and Drug Administration (FDA)). The Clinical Research Associate (CRA) / on site monitor and auditor may review all CRFs/eCRFs, and written informed consents. The accuracy of the data will be verified by reviewing the documents described in Section 8.3.1.

8.4 LISTEDNESS AND EXPEDITED REPORTING OF ADVERSE EVENTS

8.4.1 Listedness

To fulfil the regulatory requirements for expedited safety reporting, the sponsor evaluates whether a particular adverse event is "listed", i.e. is a known side effect of the drug or not. Therefore a unique reference document for the evaluation of listedness needs to be provided. For the BI 655066 this is the current version of the Investigator's Brochure ([U12-3042](#)). The current version of this reference document is to be provided in the ISF. No AEs are classified as listed for matching placebo, study design, or invasive procedures.

8.4.2 Expedited reporting to health authorities and IECs/IRBs

Expedited reporting of serious adverse events, e.g. suspected unexpected serious adverse reactions (SUSARs) to health authorities and IECs/IRBs, will be done according to local regulatory requirements. Further details regarding this reporting procedure are provided in the Investigator Site File.

Proprietary confidential information.

© 2018 Boehringer Ingelheim International GmbH or one or more of its affiliated companies. All rights reserved.

This document may not - in full or in part - be passed on, reproduced, published or otherwise used without prior written permission.

8.6 COMPLETION OF TRIAL

The EC/competent authority in each participating EU member state needs to be notified about the end of the trial (last patient out, unless specified differently in [Section 6.2.3](#) of the CTP) or early termination of the trial.

Proprietary confidential information.

© 2018 Boehringer Ingelheim International GmbH or one or more of its affiliated companies. All rights reserved.

This document may not - in full or in part - be passed on, reproduced, published or otherwise used without prior written permission.

10. APPENDICES

10.1 PASI SCORE DEFINITION AND INSTRUCTIONS

The PASI score is an established measure of clinical efficacy for psoriasis medications. ([R96-3541](#))

To calculate the PASI score, the four main body areas are assessed: **head (h), trunk (t), upper extremities (u) and lower extremities (l)**. These correspond to 10, 30, 20 and 40% of the total body area respectively.

The **area of psoriatic involvement** of these four areas (Ah, At, Au, and Al) is given a numerical value: 0 = no involvement, 1 = <10%, 2 = 10 to <30%, 3 = 30 to <50%, 4 = 50 to <70%, 5 = 70 to <90%, and 6 = 90 to 100% involvement.

The **signs of severity, erythema (E), infiltration (I) and desquamation (D)** of lesions are assessed using a numeric scale 0-4 where 0 is a complete lack of cutaneous involvement and 4 is the severest possible involvement; scores are made independently for each of the areas, h, t, u and l and represents a composite score for each area. An illustration of judging erythema follows: 0 = no erythema, 1 = slight erythema, 2 = moderate erythema, 3 = striking erythema, and 4 = exceptionally striking erythema.

The PASI score is calculated according to the following formula:

$$\text{PASI} = 0.1(Eh+Ih+Dh)Ah + 0.3(Et+It+Dt)At + 0.2(Eu+Iu+Du)Au + 0.4(El+Il+Dl)Al$$

10.2 STATIC PHYSICIAN'S GLOBAL ASSESSMENT (SPGA) OF THE NPF PSORIASIS SCORE (NPFPS)

The NPF Psoriasis Score (NPFPS) was devised by the National Psoriasis Foundation Medical Advisory Board to address deficiencies inherit in the PASI, and to provide a dynamic, reproducible, and easy 5-component method to measure clinically significant improvement in trials of new or existing psoriatic therapies ([R03-1207](#), [R03-1208](#)). The static Physician Global Assessment (sPGA) is one of five components of the NPFPS, and may be used independently ([R03-1207](#), [R03-1208](#)).

The primary sPGA variable to be analysed will be the proportion of patients that are "clear or almost clear". This has been shown to correlate well with PASI75 or higher score.

For patients to be considered "clear," the average of the 3 components must be zero (with standard rounding rules, i.e., 0.333 rounds to 0) and the score for thickness must equal zero.

For patients to be considered "almost clear," the average of the 3 components must be 1 (with standard rounding rules, i.e., 1.333 rounds to 1) and each of the individual components must be less than 3 (in other words, each of the 3 components must be equal 0, 1, or 2).

Additionally, patients with an average of the 2 components equal to zero but with a thickness score of 1 will be considered as "almost clear."

Static Physician Global Assessment (averaged over all lesions)

0	clear	= cleared, except for residual discoloration
1	almost clear	= majority of lesions have individual scores for thickness (a), erythema (b) and scaling (c) that averages 1.
2	mild	= majority of lesions have individual scores for thickness (a), erythema (b) and scaling (c) that averages 2.
3	moderate	= majority of lesions have individual scores for thickness (a), erythema (b) and scaling (c) that averages 3.
4	marked	= majority of lesions have individual scores for thickness (a), erythema (b) and scaling (c) that averages 4.
5	severe	= majority of lesions have individual scores for thickness (a), erythema (b) and scaling (c) that averages 5.

(a) Thickness (averaged over all lesions)

- 0 = no evidence of plaque elevation
- 1 = minimal plaque elevation, ≈ 0.25 mm
- 2 = mild plaque elevation, ≈ 0.5 mm

Proprietary confidential information.

© 2018 Boehringer Ingelheim International GmbH or one or more of its affiliated companies. All rights reserved.

This document may not - in full or in part - be passed on, reproduced, published or otherwise used without prior written permission.

3 = moderate plaque elevation, \approx 0.75 mm
4 = marked plaque elevation, \approx 1 mm
5 = severe plaque elevation, \approx 1.25 mm or more

Thickness in the sPGA may be graded with the aid of a reference card, which has embossed elevations ranging from 0 to 1.25 mm that increase linearly at 0.25 mm increments corresponding to varying levels of thickness (0-5) for each target lesion. The dermatologist should select 3 or more representative lesions (e.g., lesions not on the face, scalp, intertriginous areas or only on elbows or knees) at the time of the visit and measure their thickness. These can be averaged to derive the thickness score. The investigator should assess the average degree of thickness and then select the number that most represents this. For any assessments that fall half way between any two numbers on the scale, the investigator will be told to always round up to the higher number. This would result in then the following implied range: 0 = 0 to <0.125 mm, 1 = ≥0.125 to <0.375 mm, 2 = ≥0.375 to <0.625 mm, 3 = ≥0.625 to <0.875 mm, 4 = ≥0.875 to <1.25 mm and 5 = ≥1.25 mm.

(b) Erythema (averaged over all lesions)

0 = no evidence of erythema, hypo- or hyper-pigmentation may be present
1 = faint erythema
2 = light red coloration
3 = moderate red coloration
4 = bright red coloration
5 = dusky to deep red coloration

(c) Scaling (averaged over all lesions)

0 = no evidence of scaling
1 = minimal; occasional fine scaling over less than 5% of the lesion
2 = mild; fine scaling predominates
3 = moderate; coarse scaling predominates
4 = marked; thick, non-tenacious scaling predominates
5 = severe; very thick tenacious scaling predominates

